#### 9.1.7 POST-OPERATIVE PROMS

- 1. Follow-up timepoint
  - a. 6 months
  - b. 1 year
  - c. 2 years
  - d. 5 years
- 2. Date completed
- 3. MOXFQ
- 4. AOS
- 5. EQ5D-5L

#### 9.1.8 WITHDRAWAL OR DISCONTINUATION

- 1. Date of withdrawal or discontinuation
- 2. Date of last visit assessment

- 3. Reason for withdrawal or discontinuation
  - a. Patient withdrew
  - b. If in the PI/CI opinion, continuation in the study would be detrimental to the patient's well-being.
  - c. Lost to follow-up
  - d. Patient has died (please ensure AE/SAE form has been completed)
  - e. Other (please specify)

## 10. ADVERSE EVENTS AND DEVICE REMOVAL EVENTS

The PI and research delivery team at each site are required to document all AEs and SAEs occurring within a 90-day post-operative period including date of occurrence, type of AE/SAE, treatment and outcome. Following this, only AE/SAEs relating to the ankle joint or related structures (i.e., ankle and surrounding structures, Achilles tendon, calf muscle, hindfoot and midfoot proximal to mid metatarsals) need to be reported.

All AEs and SAEs will need to be reported to the study management team and to host Research & Development (R&D) department according to local guidelines. Any unanticipated device of study related SAEs will need to be notified to the HRA and REC.

An SAE report form should be completed by the PI and research delivery team within 24 hours of the site's knowledge.

The PI will keep a copy of the AE/SAE information in their electronic Investigator Site File (eISF) at their site. If at the time of sending the report, all details are not available, then one must send it with the available data and then seek to obtain complementary information. The complementary information will be sent by the PI or research delivery team of the study site to the sponsor, Northumbria Healthcare NHS Foundation Trust, and study management team, South Tees Hospitals NHS Foundation Trust, as soon as it will be available.

In case of component revisions product related issues and/or SAEs, Stryker will be notified of the event.

Death will be both reported in the SAE report form and in the termination form part of the CRFs.

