# 1. STUDY SUMMARY

Full Title:	INFINITY™ with ADAPTIS™ and EVERLAST™ technology total ankle replacement follow-up			
Short Title:	UK ADAPTIS™ Study			
Phase:	Phase 4, Post-Market			
Design:	A prospective multi-centre cohort series of INFINITY™ with ADAPTIS™ and EVERLAST™ Technology with Poly Insert for patients requiring primary total ankle replacement (TAR) i.e. Total Ankle Arthroplasty (TAA).			
	Patients meeting the criteria for the study will be asked to enrol by providing written informed consent.			
	The patients will be monitored clinically by post-operative follow-up examinations and Patient reported outcome measures (PROMs) (Manchester Oxford Foot & Ankle Questionnaire (MOXFQ), Ankle Osteoarthritis Scale (AOS), EQ5D-5L).			
Duration:	The study will have a minimum 12-month recruitment period and up to 5 years post-operative follow-up.			
Setting:	It is anticipated around 10 UK NHS Hospital Trusts regularly performing TAA/TAR will participate.			
Sample Size:	Minimum of 200 patients.			
Inclusion Criteria:	
 
Male or non-pregnant female over the age of 21 years with a diagnosis of end stage ankle arthritis and requiring primary TAA/TAR and is suitable for the use of the ADAPTIS TAA/TAR.
 
Patients who are physically and mentally willing and able to comply with the post-operative follow-ups and an appropriate rehabilitation schedule.
 
Patient can understand and provide written consent.
 
			
Exclusion Criteria:	
 
Patients with previous ankle arthrodesis or Patients who require revision of previously implanted TAA/TAR.
 
Any patients presenting with clinically relevant conditions prior to implantation, that would contraindicate implantation of a TAA/TAR.
 
			

Indication:	Intended use: It is intended to give a patient limited mobility by reducing pain, restoring alignment, and replacing flexion and extension movement in the ankle joint.				
	Indications for use:				
	
 
Patients with ankle joints damaged by severe rheumatoid, post-traumatic, or degenerative arthritis.
 
				
	
 
Patients with a failed previous ankle surgery.
 
				
Intervention:	INFINITY™ with ADAPTIS™ and EVERLAST™ technology with Poly Insert for patients requiring primary TAA/TAR.				
Objectives:	The primary objectives of the study are to assess device survivorship and performance using rates of re-operation or revision and PROMs over a 5-year post-operative period.				

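### After day 90 the AE rule covers only the ankle region, which conflicts with Section 10's own unlimited rules and can leave late, related, non-ankle SAEs unreported

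*Protocol*

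**What the plan says.** Section 10 sets two periods. In the first, sites must "document all AEs and SAEs occurring within a 90-day post-operative period". For the rest of follow-up it states: "Following this, only AE/SAEs relating to the ankle joint or related structures" need to be reported. A bracketed list defines those structures purely by anatomy, from the calf to the midfoot. It gives no exception for seriousness, relatedness or death.

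The same section then gives three rules that carry no time or anatomical limit:

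- General reporting: "All AEs and SAEs will need to be reported to the study management team".
- Notification: "Any unanticipated device of study related SAEs will need to be notified to the HRA and REC". The word after device reads as a typing error for 'or'.
- Death: "Death will be both reported in the SAE report form and in the termination form part of the CRFs".

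Section 9.1.8, the withdrawal form, lists death as a reason and prompts for the other form: "Patient has died (please ensure AE/SAE form has been completed". Section 10.1 makes the event date the first item on the AE form. The schedule in Section 2 marks adverse events as collected at any time. Section 1 gives "up to 5 years post-operative follow-up".

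**The concern.** The filter after day 90 works by body region, whereas the notification rule works by relatedness and expectedness. The two do not select the same events. A serious systemic event that follows a late ankle re-operation may be related to the procedure, yet it lies outside the listed structures. Under the 90-day sentence the site need not report it. Under the notification rule it must go to the HRA and REC if it is unanticipated and device- or study-related.

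Three uses of the data depend on the site reporting the event first:

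- notification to the HRA and REC;
- secondary outcome 1c in Section 5.3, which covers operative and device-related AEs and SAEs, and its summary in Section 11.2;
- the ongoing safety review in Section 11.1, on which the chief investigator decides whether the study and implantation continue.

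About 10 hospital trusts are expected to take part. If they read the section differently, capture of late events will differ between sites for reasons unrelated to the device.

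**Working it through.** The plan states no figure on this point, so there is none to reproduce. The check is a comparison of the rules, plus the share of follow-up that each one governs.

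**Step 1. How the rules treat an event after day 90**

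| Late event | 90-day sentence | Other rule | Result |
|---|---|---|---|
| Ankle-region AE or SAE, including loosening, subsidence, implant failure, deep infection | Report | Consistent | No gap |
| Revision or re-operation of the ankle | Report | Coded and dated in Section 10.1 | No gap |
| Death from a non-ankle cause | Need not report | Section 10 death rule; prompt in 9.1.8; event date in 10.1 | Wording conflict, but a specific rule covers it |
| Unanticipated device- or study-related SAE outside the listed structures | Need not report | Section 10 notification rule says it must be notified | Conflict, precedence not stated |
| Anticipated device- or procedure-related SAE outside the listed structures | Need not report | Falls within outcome 1c; only the general reporting rule could reach it | Conflict with the general rule, precedence not stated |
| Unrelated SAE outside the listed structures | Need not report | Only the general reporting rule could reach it | A legitimate limit on late collection |

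The general reporting rule carries less weight than the other two. It can be read as meaning all events that fall within the scope already set. The notification rule is harder to read that way, because it opens with 'Any' and defines its own scope.

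**Step 2. Share of follow-up under the restricted rule**

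Inputs: a 90-day full window (Section 10), the primary time point at 2 years (Section 5.2) and follow-up to 5 years (Section 1). Nominal days are 2 × 365 = 730 and 5 × 365.25 ≈ 1826. Visit windows are ignored.

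- To 2 years: 90/730 = 12.3% under full capture; (730 − 90)/730 = 640/730 = 87.7% under the filter.
- To 5 years: 90/1826 = 4.9% under full capture; (1826 − 90)/1826 = 1736/1826 = 95.1% under the filter.

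These are shares of time, not of events. Early complications may cluster within the first 90 days, and the protocol gives no rate from which to count late, related, non-ankle SAEs.

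**The case against.** The strongest reply is that a specific rule qualifies a general one. Read that way, the notification and death rules stand as exceptions to the 90-day sentence and the obligation already exists. A site could also treat a complication of ankle surgery as relating to the ankle even when it shows elsewhere in the body. Restricting late collection to the joint region is a reasonable choice in a post-market cohort, and almost all device failures show themselves there.

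Much of this stands. It does not remove the problem, because the bracketed list is strictly anatomical and nothing links the 90-day sentence to the later rules. Staff who stop at that sentence would be following the text.

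Pulmonary embolism is a natural example, but it needs care. Section 10.1 lists it among events not related to the implant, so a missed case would thin the operative summary and not the device-related one.

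A reader might also infer that deaths, or dates of death, will be lost, since 9.1.8 asks for "Date of withdrawal or discontinuation" and a last-visit date but lists no date of death. The documents do not support that. Death has its own rule without a time limit, the withdrawal form prompts for the AE/SAE form, and that form starts with the event date. For a death, that is the date of death. An assumed count of deaths over 5 years would show how many occur, not how many are missed, and a further date field would largely duplicate an existing one.

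**Conclusion.** The contradiction is real and should be corrected, but it is narrow. Section 10 tells sites that after 90 days a non-ankle event need not be reported, and also that any unanticipated related SAE must be notified. It does not say which governs. The exposed group is late SAEs that are related to the device or procedure and lie outside the listed structures.

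The restricted rule applies for about 88% of the 2-year period and 95% of the 5-year period. The number of events at stake is probably small, but the documents do not allow an estimate. Device survivorship is not threatened, because revisions and re-operations remain reportable throughout.

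The conclusion assumes that an event must first be reported by the site before it can be assessed for notification. Section 10 implies this by placing documentation with the site team, but does not state it.

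**What to change.** Reconcile the sentences in Section 10 by amending the 90-day rule. After day 90, sites would report:

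1. ankle-region AEs and SAEs, as now;
2. any SAE judged device- or procedure-related, wherever it is located;
3. all deaths.

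Item 2 is deliberately wider than unanticipated events, because outcome 1c covers operative and device-related SAEs whether anticipated or not. Item 3 only makes explicit what the death rule already requires. In the same edit, correct the notification rule so that it reads device or study related.

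No new CRF field is needed. The cost is one amended sentence, one corrected word and a few extra reports per site. The restriction on unrelated late events stays in place.

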### **10.1 AE REPORTING**

- 1. Date of AE/SAE
- Glazebrook classification

- a. Low grade
  - i. Intra-operative bone fracture
  - ii. Wound healing problems
- b. Medium grade
  - i. Technical error
  - ii. Subsidence
  - iii. Post-operative bone fracture
- c. High grade
  - i. Deep infection
  - ii. Aseptic loosening
  - iii. Implant failure
- d. Not related to the implant
  - i. Deep vein thrombosis
  - ii. Pulmonary embolism
  - iii. Death
- e. Other
- 3. COFAS reoperation and revision coding:
  - a. No reoperation within or surrounding the ankle
  - b. Isolated hardware removal around the ankle
  - Repeat operation outside the ankle replacement or arthrodesis (e.g., osteotomy, fusion or ligament repair) but related to the replacement or arthrodesis
  - d. Ankle gutter or heterotopic ossification debridement without exchange of metal components, with or without intact polyethylene exchange
  - e. Exchange of polyethylene liner as a result of polyethylene failure
  - f. Debridement of an osteolytic cyst without exchange of metal components, with or without intact polyethylene exchange
  - g. Deep infection or wound complication requiring operative debridement (without exchange of metal components in ankle replacement), with or without intact polyethylene exchange
  - h. Revision of arthrodesis due to malposition or non-union (no infection)
  - i. Implant failure leading to revision of metal components due to aseptic loosening, component fracture, or malposition (no infection)
  - j. Revision of metal component(s) secondary to infection
  - k. Amputation above the level of the ankle
- 4. Date of re-operative/revision

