Outcomes:	Primary outcomes are functional status (MOXFQ) at 2-year post-operative and device survivorship at 2 years.				
	Secondary outcomes are:				
	
 
Survivorship of the components at 2 years and 5 years post-operative.         
 
Revision of any components (excluding incidental polyethelene exchange for infection).
 
Re-operation without component exchange.
 
Type and frequency of adverse events (AEs), specifically operative and device related AEs and serious AEs (SAEs).
 
 
 
				
	
 
Functional status, pain and disability (MOXFQ & AOS), and health-related quality of life (EQ5D-5L) at 6 months, 1 year, 2 years, and 5 years post-operative.
 
				
	
 
Clinical assessment at 6 weeks, 6 months, 1 year, 2 years, and 5 years.
 
				
	
 
Radiographic assessments at 6 months,1 year, 2 years, and 5 years.
 
				
Analysis of Results:	The analyses will be mainly descriptive. Continuous data will be summarised using means and standard deviations (or median, interquartile range, minimum and maximum as appropriate). Categorical data will be summarised using counts and percentages. Linear or logistic regression models (as appropriate depending on the outcome) will be used to				

evaluate the influence of patient, clinical and surgical factors on outcomes.

AEs and SAEs will be summarised descriptively, whether they are operative or device related.

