### **5.2 PRIMARY OUTCOMES**

Primary outcomes are functional status (MOXFQ) at 2-year post-operative and device survivorship at 2 years.

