### **5.3 SECONDARY OUTCOMES**

Secondary outcomes are:

- 1. Survivorship as removal or exchange of one or more of the components (excluding incidental polyethylene exchange for infection) at 2 years, 5 years and post-operative.
  - a. Revision of any components (excluding incidental polyethelene exchange for infection).
  - b. Re-operation without revision
  - c. Type and frequency of adverse events (AEs), specifically operative and device related AEs and Serious AEs (SAEs).
- 2. Functional status, pain and disability (MOXFQ & AOS) and health-related quality of life (EQ5D-5L) at 6 months, 1 year, 2 years, and 5 years post-operative.
- 3. Clinical assessment 6 weeks, 6 months, 1 year, 2 years, and 5 years postoperative.
- 4. Radiographic assessments at 6 months 1 year, 2 years, and 5 years postoperative.

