### 8. DEVICE DESCRIPTION

The INFINITY™ with ADAPTIS™ and EVERLAST™ technology Total Ankle System is a two-piece semi-constrained fixed-bearing, bone-sparing total ankle prosthesis that restores mobility to a failing ankle joint. The System consists of a highly polished metal talar dome, a titanium alloy tibial tray, and Poly Insert (an ultra-high molecular weight polyethylene tibial insert). The components are available in a variety of sizes and design configurations intended for both primary and revision applications.

Through the advancement of partial and total joint replacement implants, the surgeon has been provided with a means of restoring mobility, correcting deformity, and reducing pain for man patients. While the prostheses used are largely successful in attaining these goals, it must be recognised that they are manufactured from a variety of materials and that any joint replacement system, therefore, cannot be expected to withstand activity levels and loads as would normal healthy bone. In addition, the system, including the implant/bone interface, will not be as strong, reliable, or durable as a natural human joint.

This system is manufactured according to International Conference on Harmonisation (ICH) Good Clinical Practices (GCP) in accordance with applicable Good Manufacturing Practices (GMP) and ISO 14155:2020 through relevant manufacturing and related validation processes.

The INFINITY™ with ADAPTIS™ and EVERLAST™ technology Total Ankle System Tibia Tray and Talar Dome are manufactured using an improved process known as Direct Metal Laser Sintering, also known as ADAPTIS™ 3D printing, produces a porous metal surface made from Ti6Al4V (Tibia Tray) and CoCr (Talar Dome), respectively, to interface with the bone.

The INFINITY™ with ADAPTIS™ Technology modular articular inserts are manufactured from EVERLAST™ Highly Crosslinked Polyethylene blended with Vitamin E. The propriety manufacturing process has been optimised to develop an enhanced ankle insert with retained material strength, reduced oxidation potential, and improved wear resistance. They are available in 8 sizes, with 4 thicknesses per size.

The INFINITY™ with ADAPTIS™ and EVERLAST™ technology Total Ankle System includes:

- INFINITY™ with ADAPTIS™ Technology Tibial Tray
- INFINITY™ with ADAPTIS™ Technology Chamfer-Cut Talar Component
- INFINITY™ with ADAPTIS™ Technology Flat Cut Talar Dome
- INFINITY™ EVERLAST™ Poly Insert

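### Re-operation codes d and f in protocol section 10.1 pool debridement with and without insert exchange, so the section 5.3 survivorship failure cannot be derived from the coded items listed there

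*Protocol*

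**What the plan says.** Section 5.2 of the protocol states: "Primary outcomes are functional status (MOXFQ) at 2-year post-operative and device survivorship at 2 years". It does not define survivorship. The definition is in section 5.3, where survivorship is described "as removal or exchange of one or more of the components (excluding incidental polyethylene exchange for infection) at 2 years, 5 years and post-operative". The accompanying non-failure category is "Re-operation without revision" in section 5.3 and "Re-operation without component exchange" in the study summary, so the dividing line is whether a component was exchanged.

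Section 8 lists the components: "The System consists of a highly polished metal talar dome, a titanium alloy tibial tray, and Poly Insert". The insert therefore counts as one of them.

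Section 10.1, item 3, records re-operations with the COFAS codes. Code d is "Ankle gutter or heterotopic ossification debridement without exchange of metal components, with or without intact polyethylene exchange". Code f is "Debridement of an osteolytic cyst without exchange of metal components, with or without intact polyethylene exchange". Code g, for deep infection or a wound complication needing debridement, carries the same with-or-without qualifier. Code e covers a liner exchanged because the polyethylene failed. Code i covers non-infected revision of metal components and names three causes: aseptic loosening, component fracture and malposition. No item listed in section 10.1 asks which component was exchanged or removed.

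**The concern.** The failure definition and the codes divide re-operations at different places. Section 5.3 divides them by exchange of any component. Codes d and f divide them by exchange of a metal component and leave the insert open. If an intact insert is swapped during a non-infective gutter or cyst debridement, that patient has failed under 5.3. If the same debridement leaves the insert in place, the patient has not. Both receive the same code.

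A primary outcome is at stake. An analyst working from the coded data must count every d and f case as a failure, or none of them, or go back to narrative text. The first two choices misclassify some patients unless all the cases happen to fall on one side. The third depends on what each of about 10 sites chose to write down. A statistical analysis plan can state a mapping rule, but no rule can separate cases that carry the same code.

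**Working it through.** **Step 1. Map each code in section 10.1, item 3, to the event in section 5.3.**

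| Code | Content (paraphrased) | Status under 5.3 |
|---|---|---|
| a, b, c | No re-operation; isolated hardware removal; operation outside the replacement | Not a failure |
| d | Gutter or heterotopic ossification debridement, insert exchanged or not | **Indeterminate** |
| e | Liner exchange for polyethylene failure | Failure |
| f | Osteolytic cyst debridement, insert exchanged or not | **Indeterminate** |
| g | Debridement for deep infection or wound complication, insert exchanged or not | Infection with incidental exchange: not a failure. Non-infective wound complication: **indeterminate** |
| h | Revision of an arthrodesis | Not applicable |
| i, j | Metal revision, non-infected or infected | Failure |
| k | Amputation above the ankle | Device lost with the joint; the protocol does not say how it is counted |

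Code e does not resolve d and f, because it is limited to polyethylene failure while d and f concern an intact insert. The infection exclusion in 5.3 does not resolve them either, because d and f are not infection codes.

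**Step 2. Look for another listed item that separates the cases.** Item 4 of section 10.1 is a date that serves re-operation and revision alike. Section 10 asks sites to document treatment and outcome, and section 10.2 has an entry for the action taken. Either could mention an insert exchange, but neither is a defined component item.

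**Step 3. Scale.** The protocol gives no survivorship, revision or debridement rate, so there is no stated figure to reproduce. The one input is the minimum of 200 patients (section 6.1). All event counts below are assumptions.

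Effect of one ambiguous patient on crude survivorship: 1 / 200 = 0.5 percentage points.

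All-or-none range for m ambiguous patients: m × 0.5 points.

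- m = 2: 1 point
- m = 4: 2 points
- m = 8: 4 points

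Crude 2-year survivorship with exact (Clopper-Pearson) 95% intervals:

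| Clear failures | Ambiguous cases | None counted as failure | All counted as failure |
|---|---|---|---|
| 2 | 2 | 198/200 = 99.0% (96.4 to 99.9) | 196/200 = 98.0% (95.0 to 99.5) |
| 4 | 4 | 196/200 = 98.0% (95.0 to 99.5) | 192/200 = 96.0% (92.3 to 98.3) |
| 4 | 8 | 196/200 = 98.0% (95.0 to 99.5) | 188/200 = 94.0% (89.8 to 96.9) |

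These ranges are bounds. The actual error depends on how many of the m cases included an exchange. If 2 of 4 did, either mapping misclassifies 2 patients and is off by 2 × 0.5 = 1 point.

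**Step 4. Secondary gap.** Code i names three causes and code j covers infection. Item 3 has no *other* option, although the complication classification in item 2 has one. Non-infected metal removal for another reason, unexplained pain for example, is a failure under 5.3 but has no clearly fitting code.

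**The case against.** The strongest reply is that the information is recoverable. An insert exchange is a treatment, and section 10 requires treatment to be documented and missing details to be sent later. Section 10.2 records the action taken. Section 13 opens medical records to the study management team, and section 6.5 continues collection of hospital information after withdrawal unless the patient refuses. If only a handful of cases are ambiguous, checking them is a modest task. This stands. A reader might infer that the endpoint cannot be obtained from the form at all, or is lost for good; the documents do not support that. They support only that the coded items do not give it. Linkage to the National Joint Registry is less help, since section 6.3 describes it as future, with agreement in principle still to be sought.

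Sections 9 and 10 also outline the forms rather than reproduce them, and the REDCap screens may hold more. That too is fair: the finding is about what the protocol lists.

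The size rests on assumed counts and is an all-or-none bound. It should not be read as an expected bias.

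A reader might also object that only one re-operation date is listed. That does not hold: section 10.1 is completed for each event, so one date per form is enough.

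Finally, the COFAS coding is not at fault in itself. The mismatch comes from pairing it with a different failure definition and no component item. Whether code i could be applied more broadly in practice depends on the cited coding source, which is not at hand, so that gap remains a secondary point.

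**Conclusion.** The mismatch is real and touches a primary outcome. As listed, codes d and f, and code g for a non-infective wound complication, each hold both failures and non-failures under section 5.3. Two-year survivorship therefore cannot be derived from the coded items in section 10.1 and would rest on narrative text or record review.

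The firm figure is 0.5 percentage points of crude survivorship per ambiguous patient at 200 patients. The total is unknown; 1 to 4 points is the all-or-none range for an assumed 2 to 8 cases. Where failures are few, even this matters: in the 2-and-2 and 4-and-4 examples the failure count doubles with the mapping chosen.

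The conclusion assumes that the 5.3 definition governs the primary outcome, since section 5.2 gives none, and that the form holds no component item beyond those listed. The unclear home for other non-infected metal removals is a lesser gap in the same list.

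**What to change.** In section 10.1, add to each re-operation record:

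- tibial tray, talar component and insert, each marked retained, exchanged or removed;
- infection, yes or no;
- an *other reason* option for revision or removal of metal components.

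State that the section 5.3 event is derived from these items, and keep the COFAS code alongside them. Every re-operation then records whether and which components were exchanged, and codes d and f no longer leave a range. A mapping rule alone would be a weaker substitute: it would make the analysis reproducible, but by assigning all cases under a code to one side it would depart from the 5.3 definition.

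The cost is a few REDCap fields on a form already completed for each event, with negligible site time. Adding them before re-operations accumulate avoids a retrospective review of operation notes.

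### Re-operation codes d and f (and g where there is no infection) each mix survivorship failures with non-failures, and no dedicated item records whether the insert was exchanged

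*Protocol*

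**What the plan says.** Section 5.2 makes survivorship a primary outcome without defining the event: "Primary outcomes are functional status (MOXFQ) at 2-year post-operative and device survivorship at 2 years". The only definition is in 5.3, item 1: "removal or exchange of one or more of the components (excluding incidental polyethylene exchange for infection". The same exception for infection is repeated in 5.3 item 1a and in the Study Summary. Section 5.3 lists a separate outcome, "Re-operation without revision", which the Study Summary words in terms of no component having been exchanged.

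Section 8 settles that the insert is a component: "The System consists of a highly polished metal talar dome, a titanium alloy tibial tray, and Poly Insert".

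Re-operations are recorded in 10.1, item 3, by a single lettered COFAS code. Two of the codes do not concern infection and leave the insert open:

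- Code d: "Ankle gutter or heterotopic ossification debridement without exchange of metal components, with or without intact polyethylene exchange".
- Code f: "Debridement of an osteolytic cyst without exchange of metal components, with or without intact polyethylene exchange".

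Code g covers debridement for deep infection or for a wound complication, and also leaves the insert open. Code e gives insert exchange a code of its own, but only when the polyethylene has failed. The only other operation item in 10.1 is a date, shared by re-operations and revisions.

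**The concern.** What separates a survivorship failure from a re-operation without revision is whether a component was exchanged. For gutter, ossification or cyst debridement, the metal is by definition left alone, so the insert alone decides, and the code leaves the insert open. One letter then stands for both an event and a non-event of a primary outcome.

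Two reported results are exposed: survivorship at 2 years (primary) and 5 years (secondary), and the count of re-operations without revision. A misplaced case moves them in opposite directions. A statistical analysis plan can say which codes count as events, but it cannot separate cases that the code has merged. The gap is in data capture, and the protocol is where that is specified.

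**Working it through.** No figure in the protocol depends on this point, and the sample size of 200 comes with no event rate or precision target, so there is nothing to reproduce. The check is a mapping of codes to the definition, followed by a simple bound.

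**Step 1. Each code in 10.1 item 3 against the 5.3 definition**

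| Code | Content | Survivorship event under 5.3? |
|---|---|---|
| a, b, c | No re-operation; hardware removal around the ankle; operation outside the replacement | No |
| d | Gutter or ossification debridement, metal left | Yes if insert exchanged, no if left: undetermined |
| e | Insert exchanged because it failed | Yes |
| f | Cyst debridement, metal left | Yes if insert exchanged, no if left: undetermined |
| g | Debridement for deep infection or wound complication, metal left | Deep infection with incidental insert exchange: no. Wound complication without infection: undetermined |
| h | Revision of an arthrodesis | Concerns arthrodesis, not a replacement |
| i, j | Metal component revised, without or with infection | Yes |
| k | Amputation | Not addressed by the definition; left aside here |

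**Step 2. Could another listed item settle d, f and g?**

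- 10.1, Glazebrook item: lists wound healing problems and deep infection separately, so it helps with infection status for code g. It says nothing about the insert.
- 10.1, date of operation: does not distinguish the two outcomes.
- 9.1.5: components and sizes, at the index operation only.
- 9.1.6: post-operative form, no component item.
- 10.2, item 2: an entry for what was done about the event. It could mention an insert exchange, but no structure is stated.
- Section 10: treatment of adverse events is to be documented. The wording is attached to the first 90 days.
- 6.3: consent to future registry linkage, with agreement still to be sought. It is not named as a source for this outcome.

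Some of these may reveal an exchange. None is specified to do so.

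**Step 3. Size per unresolved case**

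Input: N = 200, the minimum in 6.1. Crude survivorship = 1 − (events / N). One operation reclassified, in an ankle with no other failure, changes it by 1/200 = 0.005, or 0.5 percentage points.

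**Step 4. Illustration**

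The counts are assumptions, because the protocol gives none. Let c be the certain events and m the operations with unknown insert status. Survivorship lies between 1 − c/200 (none count) and 1 − (c + m)/200 (all count).

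| c | m | None count | All count |
|---|---|---|---|
| 4 | 2 | 98.0% | 97.0% |
| 4 | 4 | 98.0% | 96.0% |
| 4 | 10 | 98.0% | 93.0% |
| 8 | 2 | 96.0% | 95.0% |
| 8 | 4 | 96.0% | 94.0% |
| 8 | 10 | 96.0% | 91.0% |

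For c = 4 and m = 4, the exact (Clopper-Pearson) 95% intervals are 94.96–99.45% if none count and 92.27–98.26% if all count. Known insert status and reason would reduce each range to one value.

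**The case against.** The strongest reply is that the code is not the only thing recorded. The action entry in 10.2, the treatment documentation in Section 10 and the operation notes at the sites could each show whether the insert was exchanged. That stands. A reader might infer that the event cannot be recovered from any recorded data, or that an analyst must count all d and f operations as failures or none. The documents support neither: cases can be classified one by one where the narrative or the notes are clear. What remains is that a primary outcome would rest on unstructured text from about 10 hospital trusts, or on going back to the notes.

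A second reply is that Section 11 promises a detailed analysis plan before any analysis, so it is not established that the choice would be made after seeing the data. That also stands, but such a plan works with the items collected. The built REDCap forms are not shown and may hold more than 10.1 lists; the protocol does not require it.

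Third, the study is single-arm and mainly descriptive, with no performance threshold that a few cases would overturn. That limits the consequence without removing the ambiguity.

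Finally, the Study Summary's "Survivorship of the components at 2 years and 5 years post-operative" might suggest that tibial and talar survivorship must be separated, which codes i and j would not allow. The definition in 5.3 is an any-component event, no separate analysis by component is planned, and i and j both map cleanly to failure.

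**Conclusion.** The point holds for codes d and f, and for code g where a wound complication was not infected. Under 5.3 these codes pool failures with non-failures, so neither survivorship nor re-operation without revision can be read from the re-operation code, and no dedicated item records insert exchange.

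The size is 0.5 percentage points of crude survivorship per unresolved operation at N = 200. That assumes each such operation is in a different ankle with no other failure, and that all 200 are in the denominator; recruiting above the minimum would make the step smaller. The total cannot be stated, because the protocol gives no rate for these operations or for insert exchange during them. The table above is illustration, not prediction.

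The conclusion also assumes that the 5.3 definition governs the primary outcome in 5.2, which defines none of its own.

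**What to change.** For every re-operation, add to 10.1:

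1. *Polyethylene insert exchanged or removed: yes / no.*
2. If yes, *exchanged incidentally for infection: yes / no.*

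State in 5.2 and 5.3 that the survivorship event, primary and secondary, is derived from these two items together with the metal-component revision codes (i and j). Keep the COFAS code as a descriptive label. Back-fill operations already entered from the operation note.

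The cost is one or two REDCap items for the few patients who are re-operated, a sentence in the outcomes section, and a short look-back at any operations already on file. Clinical management does not change.
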